2.2 Secondary objectives

- 2.2.1 To compare the response rates using iRECIST as assessed by central review
- 2.2.2 To compare progression-free survival (PFS) and overall survival (OS) for patients treated with immunotherapy and immunotherapy plus radiotherapy
- 2.2.3 To compare the rates of treatment discontinuation at 1 year
- 2.2.4 To assess adverse events experienced by patients treated with immunotherapy and immunotherapy plus radiotherapy via the CTCAE and PRO-CTCAE.

2.2.5 To determine whether treatment effects are similar for key subgroups including those defined by the stratification variables.

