7.1 Immunotherapy with Pembrolizumab

Protocol therapy will consist of 1 cycle administered every 21 days. Treatment will continue until disease progression and no longer benefiting clinically, or unacceptable adverse event. Treatment may continue beyond disease progression per iRECIST guidelines. That is, treatment may continue beyond assessment of progressive disease (PD) provided the patient is clinically stable and felt to be continuing to benefit from therapy. A patient may be deemed clinically stable provided that no worsening of performance status has occurred, there have been no clinically relevant increases in disease-related symptoms such as pain or dyspnea that are thought to be associated with disease progression, and there has been no requirement for intensified management of disease-related symptoms, including increased analgesia, radiotherapy, or other palliative care. Repeat imaging should be obtained within 4-8 weeks if feasible, and no later than 3 months. If the subsequent scan shows additional new lesions or increase in new lesion size (sum of measurements \geq 5 mm), treatment should be discontinued.

Arm	Agent	Dose	Route	Day	Rx
A	Pembrolizumab	200 mg	IV*	Day 1	Every 3 weeks
B	Pembrolizumab + RT	200 mg + RT**	IV*	Day 1	Every 3 weeks***

* Infused over approximately 30 minutes (range: 25-40 minutes).

** Patients will receive 3 fractions of radiation to a total dose of 24 Gy (8 Gy x 3 fractions).

Administration of radiotherapy will occur to a single site for subjects randomized to the pembrolizumab and radiotherapy group.

***Radiotherapy can be initiated after the first dose of immunotherapy and must be completed before 12 weeks after first dose of immunotherapy administered.

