12.2 Criteria for Discontinuation of Protocol Treatment/Intervention

In the absence of treatment delays due to adverse event(s), treatment may continue until one of the following criteria applies:

- Disease progression per iRECIST guidelines, e.g., discontinuation due to clinical instability or additional new lesions or increase in new lesion size (see [Section 11.7](#))
- Intercurrent illness that prevents further administration of treatment
- Unacceptable adverse event(s)
- Patient decides to withdraw from the study
- General or specific changes in the patient's condition render the patient unacceptable for further treatment in the judgment of the investigator
- Clinical progression
- Patient non-compliance
- Pregnancy
- All women of child bearing potential should be instructed to contact the investigator immediately if they suspect they might be pregnant (e.g., missed or late menstrual period) at any time during study participation.
- The investigator must immediately notify CTEP in the event of a confirmed pregnancy in a patient participating in the study.
- Termination of the study by sponsor
- The drug manufacturer can no longer provide the study agent

The reason(s) for protocol therapy discontinuation, the reason(s) for study removal, and the corresponding dates must be documented in the Case Report Form (CRF).

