13.2.2 Secondary Endpoints

Tumor response using iRECIST: A patient will be determined to have a tumor response if they have a CR or PR as assessed using iRECIST by central review.

Progression-free survival (PFS): This will be the time from randomization until disease progression as assessed by the treating physician using RECIST 1.1 or death due to any cause. Patients who are alive and without documented progression will be censored at the time of last disease evaluation.

Overall survival (OS): This will be the time from randomization until death due to any cause. Patients who are not known to be dead at time of analysis will be censored at the time of their last follow-up.

Rate of treatment discontinuation at 1 year: The proportion of patients who discontinue their protocol directed treatment prior to one year from date of study registration will be determined. Patients who stop their protocol directed treatment for any reason prior to one year from study registration will be considered to have discontinued their treatment.

Adverse events: These will be assessed using CTCAE v5.0.

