13.7 Secondary Analysis Plans

A key secondary analysis will be to repeat the primary analysis that defines a tumor response by central review using iRECIST criteria.

For the secondary time-to-event endpoints, stratified Cox models will be used to compare the outcomes between the two treatment groups. This includes PFS and OS. The subgroup analyses will be done using a stratified Cox model that includes the treatment arm assignment as an explanatory variable and a separate model will be generated for each level for the subgroup of interest. The results will be summarized with a forest plot displaying the estimate of the hazard ratio and corresponding 95% confidence interval.

The rates of treatment discontinuation at one year will be summarized with a binomial point estimate and corresponding 95% confidence interval by arm. The denominator will be all patients randomized to the treatment arm and who are still alive and progression-free at one year and the numerator will be the number of patients who are alive and progression-free at one year and discontinued the protocol

treatment prior to one year. A comparison between the rates will be performed with a chi-square test or a Fisher's exact test if the assumptions of the chi-square test are violated.

Adverse events will be summarized with frequencies and relative frequencies. The maximum grade for an AE will be recorded for each patient by treatment arm. The number (percent) of patients that experience each observed adverse event will be summarized by treatment arm. In addition, the proportion of patients that experience a grade 3+, grade 4+, and grade 5 adverse event will be summarized as the number and percent of patients by treatment arm. The primary summary will be regardless of attribution. We will also do an analogous summary of the adverse events that were deemed at least possibly related to treatment.

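### The one-year treatment discontinuation rate is defined over all patients in Section 13.2.2 but computed and tested in Section 13.7 only among those alive without progression at one year

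*Combined protocol and SAP*

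**What the plan says.** The objective in Section 2.2.3 carries no restriction: "To compare the rates of treatment discontinuation at 1 year". Section 13.2.2 takes the proportion of patients who discontinue within one year of registration and specifies the event: "Patients who stop their protocol directed treatment for any reason prior to one year from study registration will be considered to have discontinued their treatment".

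Section 13.7 sets out the analysis. On the denominator it states: "The denominator will be all patients randomized to the treatment arm and who are still alive and progression-free at one year". On the numerator: "the numerator will be the number of patients who are alive and progression-free at one year and discontinued the protocol" treatment before one year. It gives a binomial estimate with a 95% confidence interval by arm and then a test: "A comparison between the rates will be performed with a chi-square test", or Fisher's exact test if the chi-square assumptions fail.

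Two other sections bear on this. Section 12.2 puts progression first among the criteria for stopping: "Disease progression per iRECIST guidelines, e.g., discontinuation due to clinical instability or additional new lesions or increase in new lesion size". Section 7.1 lets some patients stay on treatment after progression: "Treatment may continue beyond disease progression per iRECIST guidelines".

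**The concern.** An analyst who follows 13.2.2 and one who follows 13.7 would classify the same patients differently and report different rates for the same endpoint. The plan does not call the 13.7 rate supplementary, and it does not say which section governs.

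The 13.7 version also has a problem of its own. Survival and progression to one year are post-randomization outcomes. The trial asks whether radiotherapy changes response and compares PFS and OS as secondary outcomes, so it allows that treatment may shift who reaches one year without progression. If it does, the two groups that 13.7 tests are no longer the randomized groups, and a difference or its absence cannot be attributed to treatment. What is at stake is the tolerability message of one secondary endpoint.

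**Working it through.** **The two rules applied to the same patients**

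| Patient | Section 13.2.2 | Section 13.7 |
|---|---|---|
| Stops for confirmed progression at month 5 | Event | Not in numerator or denominator |
| Stops for toxicity at month 3, progresses or dies at month 10 | Event | Not in numerator or denominator |
| Progresses by RECIST 1.1, still on treatment at one year | In denominator, not an event | Dropped, if RECIST 1.1 is the criterion |
| Stops for toxicity at month 3, alive without progression at one year | Event | Event |
| On treatment at one year, no progression | In denominator, not an event | In denominator, not an event |

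The third row is conditional because 13.7 does not name its progression criterion. For PFS, 13.2.2 uses "disease progression as assessed by the treating physician using RECIST 1.1 or death due to any cause". The first two rows do not depend on that choice.

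**Patients per arm**

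The plan gives no rate, power or sample size for this endpoint, so the number per arm comes from Section 13.4. Its figure reproduces. With 20% versus 40%, one-sided alpha 0.10, 90% power, pooled variance and no continuity correction:

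n = [1.2816 × √(2 × 0.30 × 0.70) + 1.2816 × √(0.16 + 0.24)]² / 0.20² = 67.3, rounded up to 68 per arm, 136 in total.

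Inflation: 136 / 0.95 = 143.2, rounded up to 144, or 72 per arm.

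**How much of an arm deaths alone remove**

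Inputs are the median OS figures in Section 1.1. Exponential survival is my assumption. The share alive at 12 months is exp(−ln 2 × 12 / median).

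| Median OS (months) | Source | Alive at 12 months | Alive of 72 | Dead |
|---|---|---|---|---|
| 8.0 | Pembrolizumab phase III, lower 95% limit | 0.354 | 25.5 | 65% |
| 10.3 | Same, estimate | 0.446 | 32.1 | 55% |
| 11.8 | Same, upper 95% limit | 0.494 | 35.6 | 51% |
| 4.5 | Phase 1, sequential arm | 0.157 | 11.3 | 84% |
| 12.1 | Phase 1, concomitant arm | 0.503 | 36.2 | 50% |

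Patients alive but progressed are removed as well. The documents give no one-year PFS, so that further loss cannot be computed.

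**How far apart the two rates can lie**

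These inputs are assumed, because the documents give none. Let π be the share alive without progression at one year, d the share of those who had stopped, and s the share of all other patients who stopped before one year. With s = 100%, death on treatment counts as stopping.

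- Rate under 13.2.2 = (1 − π)s + πd
- Rate under 13.7 = d

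Take π from 15% to 40%, d from 10% to 30%, and s from 80% to 100%:

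- The 13.7 denominator is 72π, or 10.8 to 28.8 per arm.
- The 13.7 rate is 10% to 30%.
- The 13.2.2 rate runs from 0.60 × 0.80 + 0.40 × 0.10 = 52% to 0.85 × 1.00 + 0.15 × 0.30 = 89.5%.

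The order of the arms can reverse. Take s = 100%, with π = 20% and d = 10% in Arm A, and π = 30% and d = 20% in Arm B:

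- 13.7 gives 10% versus 20%, so Arm B looks worse.
- 13.2.2 gives 0.80 + 0.20 × 0.10 = 82% versus 0.70 + 0.30 × 0.20 = 76%, so Arm B looks better.

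This shows that a reversal is possible, not that it is likely.

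**The case against.** The strongest reply is that the restriction is deliberate. Section 13.7 states it twice, and it has a plausible purpose: to learn how often patients whose disease is controlled stop treatment. Because treatment runs until progression without further benefit or an unacceptable adverse event, an all-cause rate would overlap heavily with PFS and OS. Section 13.2.2 names no analysis population, and stopping for any reason keeps some content inside the 13.7 subset, such as adverse events, withdrawal and non-compliance. On this view the passages need only be reconciled, and the documents do not say which should give way.

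The overlap with PFS and OS is real and is a good reason to want a second measure. But the plan states no such purpose, and 13.7 does not serve it well: it loses every patient who stops for toxicity and then progresses or dies within the year. Those are stops not driven by disease, which such a measure should capture. The objective and the endpoint definition are both unrestricted, so the analysis section is the one out of line.

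The objection is right about the survival figures. The benchmark describes pembrolizumab alone, so it says little about the radiotherapy arm. It comes from a comparison with paclitaxel, docetaxel or vinflunine, whereas this trial also enrols platinum-ineligible patients. The phase 1 trial had 18 patients. The figures indicate scale and do not measure bias. It is also true that no alpha or power rests on this endpoint and that it does not enter the decision outcomes described in Section 1.1.

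**Conclusion.** The inconsistency holds on the text alone. Section 13.7, followed as written, reports and tests a quantity other than the endpoint defined in 13.2.2, in a subset selected after randomization.

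On the cited median of 10.3 months, and assuming exponential survival, about 32 of 72 patients per arm (25 to 36 over the cited interval) would be alive at one year, and fewer would remain once progressed patients are removed. The gap between the two rates and the reversal of the arms rest on assumed inputs and are illustrations only. The direction and size of any actual bias are unknown.

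The effect is confined to one secondary endpoint. The primary endpoint and the sample size are untouched, and 13.7 summarizes adverse events without this restriction. It should be corrected, but it does not threaten the trial's main conclusion.

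**What to change.** In Section 13.7:

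- Remove the survival and progression condition from numerator and denominator, and use all randomized patients, to match 13.2.2 and objective 2.2.3.
- State how death on treatment is counted.
- State how patients without required follow-up are counted. Section 12.5 requires none for patients who never start treatment, and no further follow-up for ineligible patients who continue on treatment.
- Report the between-arm difference in the one-year rate with a 95% confidence interval.
- If stopping for reasons other than progression is of interest, add it under its own name as a supportive summary. One option is the one-year cumulative incidence with discontinuation for progression and death on treatment as competing events, with the arms compared at one year. This keeps the early toxicity stops that 13.7 now loses.

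If the sponsor prefers the restricted rate, it still has to amend one of the two sections, because both cannot govern the same endpoint. The choice should be fixed before anyone sees comparative discontinuation data.

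The cost is a wording change to Section 13, which is protocol text, and minor analysis work. Section 12.2 already requires discontinuation reasons and dates on the case report form, so followed patients need no new data item.

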5.0 STUDY CALENDAR

Pre-study Testing Intervals

The pre-study testing intervals are guidelines only. Laboratory and clinical parameters during treatment are to be followed using individual institutional guidelines and the best clinical judgment of the responsible physician. It is expected that patients on this study will be cared for by physicians experienced in the treatment and supportive care of patients on this trial.

When calculating days of tests and measurements, the day a test or measurement is done is considered Day 0. Therefore, if a test were done on a Monday, the Monday one week later would be considered Day 7.

To be completed ≤ 28 DAYS before registration: All laboratory studies, history and physical.

To be completed ≤ 42 DAYS before registration: Any X-ray, scan of any type or ultrasound which is utilized for tumor measurement per protocol.

To be completed ≤ 60 DAYS before registration: Any baseline exams used for screening, or any X-ray, scan of any type or ultrasound of uninvolved organs which is not utilized for tumor measurement.

	Prior to Registration*	Day 1 of each cycle*	Post-treatment follow up**	At PD, withdrawal, or removal**
Tests & Observations				
History and physical, weight, PS***	X	X	X	X
Pulse, Blood Pressure	X	X		
ECG	X(6)			
Adverse Event Assessment-CTCAE		X	X	
Adverse Event Assessment-PRO-CTCAE	X(1)	X(1)	X	
Registration Fatigue/Uniscale Assessment	X(2)			
Laboratory Studies				
Complete Blood Count, Differential, Platelets	X	X		
Serum Creatinine	X	X		
Albumin, glucose	X	X		
AST, ALT, Alk. Phos., Bili	X	X		
TSH with reflex T4		X		
Serum or Urine hCG	X(3)			
UPC ratio/urine protein	X	A		
Staging				
Tumor Measurement	X	C	X	
CT chest/abd/pelvis	X(5)	D	D	
Correlative studies				
QOL assessment	From baseline through 24 months, see Section 6.5 .			
Tissue, blood, and urine samples	See Section 6.2 .			

- * Labs completed prior to registration may be used for day 1 of cycle 1 tests if obtained \leq 14 days prior to treatment. For subsequent cycles, labs, scans, tests and observations may be obtained \leq 72 hours prior to day of treatment.
- ** Physical examination and staging scans are required \leq 12 weeks after the end of treatment, then every 12 weeks until disease progression; thereafter, survival information is required every 3 months until 3 years following registration. See also Section 12.0.
- *** Patients receiving immunotherapy will be assessed for pulmonary signs and symptoms throughout the study.

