 - 1 The PRO-CTCAE assessment is required for all patients. If the PRO-CTCAE assessment completed prior to registration is obtained \leq 14 days prior to treatment, then the PRO-CTCAE assessment on day 1 of cycle 1 may be skipped. The PRO-CTCAE patient-completed booklet for this protocol can be found on the 'CIRB Approved Documents' tab on the CTSU website.
 - 2 To be completed after registration and \leq 21 days prior to treatment.
 - 3 For women of childbearing potential. Must be done \leq 14 days prior to initiation of study treatment.
 - 4 See Section 6.2.

- 5 Baseline scans can include either: 1) a CT, spiral CT, or MRI and bone scan, or 2) an FDG-PET scan and diagnostic CT performed with both IV and oral contrast, and the CT acquired with 5 mm or less slice thickness. Supporting documentation is to be submitted, per Section 6.1.1.
- 6 ECG prior to registration should be performed if clinically indicated.
 - A All patients receiving immunotherapy will have a urinalysis or urine protein performed \leq 72 hours prior to every dose. If urine protein is \geq 2+, 24-hour urine collection or UPC ratio will be required.
 - B Required only if signs or symptoms suggestive of metastases develop.
 - C \leq 2 days prior to each treatment if accessible to physical examination.
 - D Every 3 months until evidence of progression or relapse. If the baseline scans were a CT or MRI and bone scan, follow-up bone scans are required only for patients with bone metastases as the only site of evaluable disease, and are optional for other patients. Response assessment should include assessment of all sites of disease and use the same imaging method as was used at baseline. Bone imaging (after baseline) is required only if indicative of metastases at baseline or if signs or symptoms suggestive of metastases develop.

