To evaluate between-arm differences in patient-reported adverse events as assessed by the PRO-CTCAE from baseline through 24 months, the frequency and proportion of patients with a maximum post-baseline score greater than 0 will be compared across arms using a χ^2 test or Fisher's exact test with a nominal significance level of $\alpha = .10$. Similarly, the frequency and proportion of patients with a maximum post-baseline score greater than or equal to 3 will be compared across arms using a χ^2 test or Fisher's exact test with a nominal significance level of $\alpha = .10$. The same procedure will be applied to patients' maximum baseline-adjusted scores. Patients' maximum baseline-adjusted scores will be calculated using the method described by Dueck et al. If the patient's maximum post-baseline score is greater than his/her baseline score, then the patient's maximum baseline-adjusted score will equal his/her maximum post-baseline score; otherwise, if the patient's maximum post-baseline score is less than or equal to his/her baseline score, then the patient's maximum baseline-adjusted score will equal 0. The aforementioned analyses will be based on all available PRO-CTCAE data. However, the proportion of, and reported reasons for, missing data will be presented by time point and arm. Correlation analysis and logistic regression analysis will be used to examine whether baseline patient characteristics and prognostic factors predict missingness. As a sensitivity analysis, multiple imputation may be performed to assess the robustness of results across different assumptions about the missing data. Since a preferred or optimal statistical methodology for PRO-CTCAE data is yet to be determined, additional analyses of PRO-CTCAE data beyond those specified above may be undertaken based on the current state of the science at time of data maturity for this study.

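### The 24-month maximum PRO-CTCAE score mixes symptom risk with length of observation if time on treatment or to progression differs between arms

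*Combined protocol and SAP*

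**What the plan says.** Section 13.7 of the combined protocol and SAP sets out the between-arm analysis of "patient-reported adverse events as assessed by the PRO-CTCAE from baseline through 24 months". For a score above zero, "the frequency and proportion of patients with a maximum post-baseline score greater than 0 will be compared across arms". For a high score, "the frequency and proportion of patients with a maximum post-baseline score greater than or equal to 3 will be compared across arms". The test is a chi-square test or "Fisher's exact test with a nominal significance level of" 0.10; sidedness is not stated. The same procedure applies to a baseline-adjusted maximum, which equals the maximum if it exceeds the baseline score and is otherwise zero.

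On the data used: "The aforementioned analyses will be based on all available PRO-CTCAE data". Missing data are to be tabulated by time point and arm with reasons, predictors of missingness are to be examined, and "multiple imputation may be performed to assess the robustness of results across different assumptions about the missing data". Further PRO-CTCAE analyses are allowed but not named.

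The row "Adverse Event Assessment-PRO-CTCAE" in the section 5.0 calendar is marked before registration, on day 1 of each cycle and at post-treatment follow-up. It is not marked at progression, withdrawal or removal. A footnote adds that "The PRO-CTCAE assessment is required for all patients". Cycles last 21 days, and treatment is open-ended and may run past progression if the patient is judged to benefit (section 7.1). Off treatment, visits fall within 12 weeks and then every 12 weeks until progression, after which only survival is required (sections 5.0 and 12.3.1).

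**The concern.** A maximum can only stay the same or rise as scores are added. Here the number of scores is not fixed by design: it depends on how long the patient stays on treatment and how soon the disease progresses. The plan compares crude proportions and sets neither a common window nor an adjustment for the number of forms.

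The trial is powered for response rates of 20% versus 40% (section 13.4). If that gain occurs and carries over into longer treatment or later progression, Arm B would be asked about symptoms more often. It could then show more high maxima at the same risk per visit. Objective 2.2.4 names PRO-CTCAE, and these are its only specified between-arm tests, so a significant result could be reported as extra symptom risk from radiotherapy when part of it reflects longer observation.

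The plan's safeguards do not reach this. For a patient with a baseline score of zero, the baseline-adjusted maximum is identical to the raw maximum. The missing-data steps and imputation concern forms that were due and not returned; a form that was never scheduled is not missing.

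**Working it through.** 1. **Inputs from the documents.** Allocation 1:1; 68 evaluable patients per arm; forms every 3 weeks on treatment and about every 12 weeks afterwards until progression (a fourfold drop, 12/3); horizon 24 months (104 weeks); nominal alpha 0.10, taken as two-sided. The documents give no treatment duration, symptom frequency or within-patient correlation. Those are assumptions, shown as ranges.

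2. **The plan's own figure.** There is none for PRO-CTCAE, so the primary sample size is reproduced because it sets the N. With response rates 0.20 and 0.40, mean 0.30, one-sided alpha 0.10 and power 90% (both z = 1.2816):
 n per arm = [1.2816 × √(2 × 0.30 × 0.70) + 1.2816 × √(0.20 × 0.80 + 0.40 × 0.60)]² / 0.20² = [1.2816 × (0.6481 + 0.6325)]² / 0.04 = 67.3, rounded up to 68, hence 136. Then 136/0.95 = 143.2, rounded up to 144. Both agree with section 13.4.

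3. **How the maximum grows.** With independent visits and risk p per visit, P(threshold ever crossed in k visits) = 1 − (1 − p)^k. At p = 5% this is 18.5% for 4 visits, 33.7% for 8, 58.2% for 17 and 82.5% for 34. Within-patient correlation flattens the rise but does not remove it.

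4. **Equal risk, unequal time.** Simulated exponential treatment time capped at 104 weeks, one form per 3 weeks plus one off-treatment form, 68 per arm, and beta-distributed patient risk to induce correlation. Entries are the percentage crossing the threshold, with rejection against the 13-week arm in brackets.

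| Per-visit risk | Correlation | Median 13 wk | Median 19.5 wk | Median 26 wk |
|---|---|---|---|---|
| 5% | 0 | 26.2 | 34.0 (26%) | 40.2 (53%) |
| 5% | 0.3 | 14.2 | 16.7 (13%) | 18.5 (18%) |
| 5% | 0.5 | 10.7 | 12.0 (11%) | 13.0 (13%) |
| 10% | 0 | 42.9 | 52.3 (30%) | 59.0 (60%) |
| 10% | 0.3 | 26.5 | 30.5 (15%) | 33.3 (23%) |
| 10% | 0.5 | 20.4 | 22.7 (12%) | 24.4 (16%) |

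 With equal medians, rejection is 10–12%. The upper end occurs at 2% risk, where counts are small.

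5. **Hand check of one cell** (5%, correlation 0.3, 13 versus 26 weeks). Pooled proportion (0.142 + 0.185)/2 = 0.1635; SE = √(2 × 0.1635 × 0.8365/68) = 0.0634; shift = 0.043/0.0634 = 0.68. Rejection = P(Z > 1.645 − 0.68) + P(Z < −1.645 − 0.68) ≈ 0.167 + 0.010 = 17.7%, against 18% simulated.

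6. **Another correlation model.** With a patient random effect on the logit scale, risks of 2–8% and 3 versus 4.5 months, rejection is 17–22% at SD 1 without an off-treatment form (correlation about 0.06 at 5% risk). With that form it is 13–15% at SD 2 (about 0.23) and 12–13% at SD 3 (about 0.39). Over settings of this kind, with one off-treatment form, the summary range is about 12–20% for 3 versus 4.5 months and 15–38% for 3 versus 6 months. Full independence lies above these ranges; strong correlation lies at or just below their lower ends.

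7. **Masking.** Per-visit risk 5% in Arm A and 8% in Arm B, with Arm B stopping earlier (median 3 versus 4.5 months): power of the 24-month maximum is about 15–16%, against 21–26% using the first four cycles. Both are low, so sample size explains most of the insensitivity.

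8. **A common window.** For 13 versus 26 weeks, without an off-treatment form, limiting the maximum to 12 weeks gives rejection of 12–17% at 5–10% risk, against 15–68% for the 24-month maximum. At 30% risk the figures are 16–29% against 32–61%. With exactly four visits for everyone, rejection is 9.8–10.4%.

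**The case against.** The strongest reply is that cumulative patient-reported burden under each assigned strategy, including burden from longer treatment, is a legitimate quantity. Objective 2.2.4 asks only to assess adverse events, so a reader might infer that the planned test answers it incorrectly; the documents do not support that. The reply justifies keeping the 24-month maximum. It does not make the result a measure of symptom risk, and because off-treatment collection stops at progression, the maximum is not complete 24-month burden either.

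Second, the artefact is conditional. The 20-point gain is a minimum detectable difference in response, not a forecast of longer treatment, and the plan gives no duration figure. This stands: one cannot say that the longer-treated arm will appear more toxic, only that the test cannot separate the two explanations.

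Third, a reader might infer that nothing is collected off treatment. The calendar marks post-treatment follow-up, so collection becomes sparser and ends with progression. Including one such form dampens the effect only slightly.

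Fourth, a reader might infer that early stopping for toxicity hides that toxicity. Scores recorded before stopping remain in the maximum, and patients who stop without progression still have follow-up forms. Step 7 shows a modest loss.

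Fifth, the quality-of-life substudy compares fatigue, diarrhea, shortness of breath and pain at fixed times, continues after progression and uses mixed models (sections 6.5 and 14.1.4). That helps, but participation is optional and limited to English speakers, and it does not replace a PRO-CTCAE analysis: rash, for example, is a listed PRO-CTCAE term (section 9.1.1).

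Finally, testing only an early window would leave late events untested. This also stands, and it is why the window should be added and not substituted.

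**Conclusion.** The point holds as a conditional weakness. If time on treatment or time to progression differs between arms, the comparison of maxima mixes symptom risk with length of observation; if neither differs, it keeps close to its nominal size. Under the assumed medians of 3 versus 4.5 months, rejection at nominal 0.10 with equal per-visit risk is about 12–20%, and about 15–38% for 3 versus 6 months. These figures rest on assumed durations, per-visit risks and correlations, on stopping independent of symptoms, and on a null of equal per-visit risk; the documents fix none of these. Masking of real extra toxicity is possible but modest.

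Consequences are limited. The analysis is secondary and at nominal alpha, clinician-graded CTCAE is the safety standard, and PRO-CTCAE triggers no protocol action (section 9.0). The primary conclusion is unaffected. What is at stake is how a PRO-CTCAE difference is interpreted.

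**What to change.** Keep the 24-month maximum and its baseline-adjusted version. Before arm-level data are seen, add to section 13.7:

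- a longitudinal per-visit analysis of each threshold (GEE or mixed logistic model) with arm, visit and baseline score, stating how on-treatment and off-treatment forms enter;
- the same maximum and baseline-adjusted maximum over a common early window from the first dose, extending beyond the 12-week limit for completing radiotherapy in section 7.1, with its length fixed in advance;
- the number of completed questionnaires per patient, by arm;
- a sentence that a difference seen only in the 24-month maximum will not be read as a difference in symptom risk.

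The cost is SAP wording and some analysis code, with no change to data collection. The early window does not cover late events, and it reduces the artefact without fully removing it (step 8). The per-visit model describes patients still being assessed and needs its own missing-data assumption. The three results should therefore be reported together.
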